5.3 INCLUSION OF VULNERABLE PARTICIPANTS

Children: Patients with mutations of the insulin receptor, particularly those with biallelic mutations causing Rabson Mendenhall Syndrome, typically develop diabetes in childhood, with death often occurring in the second or third decade of life. Because this is a pediatric condition, most patients enrolled in this study will be <18 years of age. Children <5 years of age may not enroll. In our experience with the younger children, we find that their participation in serial blood tests improves greatly when they are at least 5 years of age. Also, in our experience with the patients with mutations of the insulin receptor, their initial insulin resistance is manifested as

Abbreviated Title: Effects of leptin in insulin resistance

Version Date: AM N ver. (approved 10/21/20); rev for AM O (5/5/21)

extreme hyperinsulinemia and hypoglycemia (rather than hyperglycemia) in the younger patients. We would not want to treat a young child experiencing chronic hypoglycemia.

3. The patient receives prenatal care from a high-risk obstetrician experienced in managing diabetes during pregnancy. Management of diabetes must be the primary responsibility of the patient's local health care providers, although the NIH study team will provide advice as appropriate regarding metreleptin use and use of concentrated insulin (U-500) if necessary.
4. The patient and her local health care team agree to remain in close contact with the NIH study team and respond to requests for clinical information needed to document the course of pregnancy and its outcome.

Decisionally Impaired Adults: Patients with mutations of the insulin receptor appear to have higher prevalence of cognitive impairment compared to the general population, perhaps caused by periods of prolonged, unrecognized hypoglycemia during early brain development. Therefore, it is possible that patients without capacity to consent might be candidates for this study. Because

Abbreviated Title: Effects of leptin in insulin resistance

Version Date: AM N ver. (approved 10/21/20); rev for AM O (5/5/21)

there is a prospect for direct benefit, adults who are unable to give informed consent will be eligible.

Prisoners: N/A

NIH Employees: N/A

Other vulnerable populations: N/A

5.4 LIFESTYLE CONSIDERATIONS

Diet and Exercise: A dietitian will see each patient at every visit to the Clinical Center. A simple assessment of typical diet, exercise frequency, intensity and duration will be recorded at each visit (including telehealth or telephone visits).

5.5 SCREEN FAILURES

Screen failures are defined as participants who consent to participate in the clinical trial but are not subsequently assigned to the study intervention or entered in the study. A minimal set of screen failure information is required to ensure transparent reporting of screen failure participants, to meet the Consolidated Standards of Reporting Trials (CONSORT) publishing requirements and to respond to queries from regulatory authorities. Minimal information includes demography, screen failure details, eligibility criteria, and any serious adverse event (SAE).

5.6 STRATEGIES FOR RECRUITMENT AND RETENTION

This is a single site study taking place only at NIH. We currently have enrolled 11 subjects and our anticipated accrual is 20. Patients will be recruited through the existing pool of extreme insulin resistant patients that are being followed on 76-DK-0006, “Natural History of Disorders of Insulin Resistance” Patients will also be recruited from referrals from the patients’ physicians, through physician referrals fielded through the Patient Recruitment and Public Liaison Office, or, occasionally, by self-referral.

5.6.1 Costs

No costs to subjects are anticipated.

5.6.2 Compensation

The travel expenses (within the continental United States) of patients and one guardian (for pediatric patients) to the Clinical Center will be compensated. Protocol-related medical care and follow-up of patients throughout the study including the medication will be provided by the Clinical Center free of charge. Medical care for an unforeseen reaction directly caused by either the therapy or follow-up procedures will also be provided by the Clinical Center.

6 STUDY INTERVENTION

6.1 STUDY INTERVENTIONS(S) ADMINISTRATION

6.1.1 Study Intervention Description

Metreleptin will be administered in this study under IND 60,543.

Abbreviated Title: Effects of leptin in insulin resistance

Version Date: AM N ver. (approved 10/21/20); rev for AM O (5/5/21)

6.1.2 Dosing and Administration

Metreleptin will be administered twice a day (Q12H) by subcutaneous injection at an initial dose of 0.2 mg/kg/day for both female and male subjects. The total daily dose will be administered via subcutaneous injections in two equally divided doses (12 hours apart). After 1 year on the study, if clinical benefit is seen from leptin therapy, once daily injections may be initiated. If clinical deterioration occurs with once daily injections, the patient may be returned to twice daily injections.

6.1.2.1 Dose Escalation

N/A

6.1.2.2 Dose Limiting Toxicity

N/A

6.1.2.3 Dose Modifications

Patients will monitor body weight at home weekly for the first 3 months of treatment. In addition, weight is monitored at each follow up visit. Doses of metreleptin will be adjusted based on body weight to maintain a consistent dose of metreleptin within the range of 0.18-0.24 mg/kg/day. If body weight decreases by more than 15%, then a dose reduction (by 0.02 mg/kg/day) will be made. If a dose change is made, patients will monitor body weight at home monthly for the next 3 months and additional dose adjustments will be made as needed.

6.1.2.4 Drug Administration

See above

6.2 PREPARATION/HANDLING/STORAGE/ACCOUNTABILITY

6.2.1 Acquisition and Accountability

Availability:

Amryt Pharma, PLC, is supplying Metreleptin.

Initial Drug Shipment and Re-Supply:

A signed and completed Drug Request Form must be emailed, at least 5 days prior to the expected delivery date, to Amryt Pharma Supply Chain for approval and processing at [contact]. At the end of the study, and after full accountability is performed on study drug or site closure, study drug destruction will occur at NIH.

Supply of Drug:

The study test drug will be shipped to the investigator's institution and should be checked for amount and condition of the drug received. This data will be entered into the proof of receipt letter. The proof of receipt letter should be faxed to Amryt Pharma at the number indicated on the letter and the original retained in the pharmacy files.

6.2.2 Formulation, Appearance, Packaging, and Labeling

Metreleptin will be supplied as a glass vial containing a lyophilized cake, prepared in a formulation buffer consisting of 10 mM glutamic acid, 2% glycine, 1% sucrose, and 0.01% Tween 20 to pH 4.25. Upon reconstitution with 2.2 ml of bacteriostatic sterile water, the cake will yield a 5-mg/ml concentration of Metreleptin.

Abbreviated Title: Effects of leptin in insulin resistance

Version Date: AM N ver. (approved 10/21/20); rev for AM O (5/5/21)

6.2.3 Product Storage and Stability

The study drug must be stored in a secure location under controlled conditions at the study site or pharmacy before dispensing to subjects. Metreleptin must be stored at 2-8⁰ C prior to reconstitution. It is recommended that the refrigerator be connected to a back-up power source, and a temperature alert system. Amryt Pharma must be notified if any test material is exposed to excessive or uncontrolled temperatures; possible replacement of the affected material will be considered. Study staff must be instructed in proper storage of the study drug.

Storage Temperature Monitoring:

Records of the storage conditions should be maintained throughout the study by either a continuous temperature recording system, a regularly maintained temperature alarm system or by regular visual inspection of a calibrated thermometer placed inside the refrigeration unit.

Expiration Dating:

As per standard practice for experimental biologic pharmaceuticals, Amryt Pharma will conduct periodic stability assays to monitor product stability and determine appropriate expiration dating of the study drug. The appropriate Amryt Pharma representative shall communicate this information to the investigator.

6.2.4 Preparation

Each 5 mL vial of lyophilized metreleptin (11.3 mg/vial) will be reconstituted with room temperature Bacteriostatic Sterile Water immediately prior to infusion. To reconstitute, 2.2 mL of sterile water should be injected slowly down the inside wall of the vial using a syringe and needle. Then the vial should be gently swirled and inverted until the powder is completely dissolved. THE VIAL SHOULD NOT BE SHAKEN VIGOROUSLY. The solution of reconstituted metreleptin should be clear, colorless, and free of any floating particles. Once reconstituted with bacteriostatic sterile water, remaining metreleptin can be used for up to 72 hours. Latex-free syringes should be used for all procedures with the study drug. The final concentration once reconstituted is 5 mg/ml.

6.3 MEASURES TO MINIMIZE BIAS: RANDOMIZATION AND BLINDING

N/A

6.4 STUDY INTERVENTION COMPLIANCE

Adherence to study drug will be assessed by frequency of medication refill requests as well as documentation of medication use in the medical record.

6.5 CONCOMITANT THERAPY

If patients are on glucose lowering therapy at the beginning of the study, metreleptin will be added to the existing therapy. Patients' previous therapy will be tapered to prevent hypoglycemia if necessary but doses of glucose lowering medications will not be increased during the first year of the study (at the time the primary outcome is assessed.) Glucose lowering therapies may be adjusted as clinically indicated after the first year of treatment. Patients will be standard clinical instruction about signs and symptoms of and instructions to relieve hypoglycemia.

7 STUDY INTERVENTION DISCONTINUATION AND PARTICIPANT DISCONTINUATION/WITHDRAWAL

7.1 DISCONTINUATION OF STUDY INTERVENTION

See section 7.2

7.2 PARTICIPANT DISCONTINUATION/WITHDRAWAL FROM THE STUDY

Participants are free to withdraw from participation in the study at any time upon request.

An investigator may discontinue or withdraw a participant from the study for the following reasons:

- Adverse events that are not readily explained by other causes unrelated to current protocol. Examples include:
 - Systemic life-threatening allergic reaction to metreleptin
 - Other significant medical issues that will, in the judgment of the investigators, preclude safe completion of the study.
- Noncompliance with self-monitoring requirements and Clinical Center visits
- Development of any medical problem listed in the exclusion criteria
- Significant medical issues that will in the judgment of the investigators preclude safe completion of the study. If an investigator feels it is in the subject's best interest to terminate participation, the detailed reasoning behind this decision will be documented. Examples include change in benefit-risk ratio of metreleptin treatment for an individual patient, such as:
 - Loss of efficacy of metreleptin (e.g. due to development of neutralizing antibodies)
 - Development of a medical condition that might increase risks associated with metreleptin (e.g. T-cell lymphoma, high risk thyroid cancer) in a patient not receiving dramatic clinical benefit
 - More than 8% drop in hematocrit and discontinuation recommended by Hematology Service
 - WBC count < 2500 or absolute neutrophil count < 1000 and discontinuation recommended by Hematology Service
- Death

The reason for participant discontinuation or withdrawal from the study will be recorded in the medical record.

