In a pilot study of two patients with the Rabson-Mendenhall syndromes (caused by biallelic mutations of the insulin receptor), 02-DK-0060, “Efficacy of leptin therapy in severe insulin resistance: a pilot study,” we followed two children with Rabson-Mendenhall on 10 months of recombinant leptin therapy. During the 10 months of leptin therapy, the patients had dramatic improvements (40%) in their fasting hyperinsulinemia and (50%) hyperglycemia, and overall improvements in their %HgbA1c and glucose and insulin tolerance. Three months after the medication was withdrawn, the improvements observed had deteriorated to their pre-trial baseline [1]. A follow up report published in 2013 in 5 patients who participated in the current study demonstrated that A1c decreased from $11.4 \pm 1.1\%$ at baseline to $9.3 \pm 1.9\%$ after 6 months and

9.7±1.6% after 12 months of metreleptin (P=0.007) [2]. In patients treated for 10 years, A1c declined with each cycle of metreleptin and rose with each withdrawal.

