4 STUDY DESIGN

4.1 OVERALL DESIGN

This study is designed to investigate the effect of recombinant leptin on various metabolic and hormonal abnormalities in patients with known or suspected mutations of the insulin receptor gene. These patients have low leptin levels in addition to other metabolic abnormalities. This study utilizes an open-label design, and the accrual ceiling is set at 20 patients. Cumulative changes in each patient will be compared to his/her baseline state after 6 and 12 months. The primary outcome will be assessed after 12 months of study drug. After the patient has completed one year of therapy and has shown metabolic improvement on the medication and the patient desires to continue therapy, the PI at NIH will consider extending therapy on an annual basis. The study medication is supplied through Amryt Pharma, and neither NIH nor Amryt Pharma can guarantee its availability after the study ends.

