9 STATISTICAL CONSIDERATIONS

9.1 STATISTICAL HYPOTHESIS

- Primary Endpoint(s): The primary outcome measure is improvement in HbA1c after 1 year of metreleptin,
- Secondary Endpoint(s): A number of secondary endpoints will also be studied. These include fasting blood glucose, and insulin, and C-peptide levels, as well as the glucose, insulin, and C-peptide responses to glucose tolerance tests. In the pilot study, we have observed up to a 40% reduction in fasting blood glucose, and an even greater reduction in endogenous hyperinsulinemia. While we would hope to see changes of this magnitude we cannot pre-define the extent of improvement or lack thereof that may occur.
- Exploratory Endpoints: These include body weight, body composition, creatinine clearance, and urine 24-hour protein. In addition, we will include hypothalamic pituitary parameters, LH/FSH, and thyroid function.

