9.3.2 Evaluable for objective response

Data will be analyzed as Per-Protocol Analysis Dataset: including the subset of the participants who took at least 70% of study intervention.

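### Patients who stop metreleptin before month 12 have no planned month-12 HbA1c, so the primary outcome can be missing because the drug failed or harmed

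*Combined protocol and SAP*

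**What the plan says.** Section 7.1 is where rules for a patient who stops the drug would stand. Its whole content is "See section 7.2". Section 7.2 concerns leaving the study: "An investigator may discontinue or withdraw a participant from the study for the following reasons". The list there mixes reasons for stopping a drug (life-threatening allergy, low blood counts, a changed benefit-risk balance) with reasons for ending participation (missed self-monitoring, missed visits). One example given for ending participation is "Loss of efficacy of metreleptin (e.g. due to development of neutralizing antibodies". The only recording step at exit is this: "The reason for participant discontinuation or withdrawal from the study will be recorded in the medical record".

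The endpoint is fixed at one year. Section 4.1 says "The primary outcome will be assessed after 12 months of study drug" and section 9.1 says "The primary outcome measure is improvement in HbA1c after 1 year of metreleptin". Section 9.3.2 makes the efficacy set per-protocol, "including the subset of the participants who took at least 70% of study intervention". Section 9.4.1 compares each patient with his or her own baseline and names no method for missing values.

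The schedule in section 1.3 has columns for baseline, 6 months, 1 year and later routine visits, but none for early termination or for follow-up off drug. Section 7.3 covers missed visits and patients who cannot be reached. Section 1.3 does allow local HbA1c testing when travel is not possible, and it lets outside results enter the efficacy data. It does not extend either provision to patients who have stopped the drug.

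**The concern.** When stopping the drug and leaving the study share one rule, a patient who stops at month 4 because metreleptin no longer works has no planned month-12 value. Whether the primary outcome is observed then depends on the outcome itself. This is a single-arm study with a ceiling of 20 patients, so there is no control group losing patients in a similar way, and each lost value carries weight.

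The protocol's own background suggests that the missing values would differ from the observed ones. Of the two pilot patients, section 2.2 reports: "Three months after the medication was withdrawn, the improvements observed had deteriorated to their pre-trial baseline". It adds that in patients treated for 10 years HbA1c went up whenever the drug was withdrawn. An average over those who remain on drug would then look better than the average over everyone who started.

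**Working it through.** **The plan's own figure.** Section 9.2 gives n = 6 for 80% power (change 2.1, SD 1.4, two-sided 0.05) and n = 7 for a change of 2.0 with SD 1.5. A paired t-test with the noncentral t distribution gives 71.1% power at n = 5 and 83.3% at n = 6 for the first case, and 74.3% at n = 6 and 83.4% at n = 7 for the second. Both sample sizes reproduce. They include no allowance for dropout, but they are not in dispute here.

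**What happens to a patient who stops early**

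| Step | Section | Result |
|---|---|---|
| Rule for stopping drug | 7.1 | None of its own; refers to 7.2 |
| Reasons | 7.2 | Include adverse events and loss of efficacy, as grounds for leaving |
| Data required at exit | 7.2 | The reason only |
| Later visits | 1.3, 7.3 | None planned off drug |
| Efficacy analysis | 9.3.2 | Needs 70% or more of drug taken |

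Two filters act in turn: the value is not planned, and if it were obtained most early stoppers would still be left out. Section 9.3.2 gives no denominator for the 70%. If it is 12 months of drug, the threshold is 0.70 × 12 = 8.4 months. A patient who stops at month 4 has taken 4/12 = 33% and is excluded even with a month-12 HbA1c.

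**Illustrative size.** Inputs:
- Fall in those who stay, from section 2.2: 11.4 − 9.7 = 1.7 points at 12 months (five published patients).
- Change in those who stop: 0, an assumption taken from the two pilot patients.
- Fraction stopping, f: 10%, 20% or 30%, an assumption, because the documents give no rate.

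All-treated mean = 1.7 × (1 − f). Relative overstatement by the stayers' mean = 1/(1 − f) − 1.

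| f | Stopping, of 20 | All-treated mean | Gap from 1.7 | Overstatement |
|---|---|---|---|---|
| 10% | 2 | 1.7 × 0.9 = 1.53 | 0.17 | 11% |
| 20% | 4 | 1.7 × 0.8 = 1.36 | 0.34 | 25% |
| 30% | 6 | 1.7 × 0.7 = 1.19 | 0.51 | 43% |

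More generally, if those who stop have a mean fall of s, the gap is f × (1.7 − s). It shrinks in proportion if they keep some benefit and widens if they end above baseline.

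**The case against.** **The text is permissive and silent.** Section 7.2 says what an investigator may do. No section forbids an HbA1c after stopping. Section 8.4.6 counts the 30-day window for serious adverse events from the end of dosing, while section 8.4.4 counts it from the end of participation, so the two ideas are not wholly merged. This stands: a reader might infer that the plan rules out a month-12 value, but the documents show only that none is planned. A measurement left to discretion is still a gap when the reason for exit is related to the outcome.

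**Other data exist.** A reader might also infer that nothing collected could inform the effect of starting metreleptin. The documents do not support that. HbA1c at month 6 is scheduled, section 4.1 plans a 6-month comparison, and outside results may enter the efficacy data. None of these supplies the primary endpoint for someone who has left.

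**The question is the on-drug effect.** Sections 4.1, 9.1 and 9.3.2 consistently describe a year on metreleptin, and that is a legitimate target. A month-12 value off drug would also reflect other glucose-lowering treatment, and it is unclear whether the first-year limit on increases in section 6.5 binds a patient who has stopped metreleptin. This is why an all-treated result should be added rather than substituted. It does not remove the selection: a set from which patients leave because the drug stopped working is partly chosen by the outcome.

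**The size is hypothetical.** True. The stopping rate is assumed, and the full return to baseline comes from two patients.

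**Conclusion.** The concern holds as a gap in planned data collection, reinforced by the choice of analysis set. As written, the primary outcome can be missing because of lack of effect or harm, and the reported 1-year change will describe mainly patients who stayed on drug. The likely direction favours metreleptin. Under the stated assumptions the stayers' mean exceeds the all-treated mean by 0.17 to 0.51 HbA1c points for 10% to 30% stopping. These figures show what is at stake and are not a forecast.

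Two limits apply. Collecting the value would not by itself change the reported result for early stoppers, because section 9.3.2 would still exclude them. Also, part of section 5.3, on pregnancy, is absent from the public text, so an off-drug rule specific to pregnancy could not be checked.

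**What to change.** - **Section 7.1:** state that a participant who stops metreleptin before month 12 is asked, unless consent is withdrawn, to have an HbA1c at the scheduled month-12 date. Accept a local draw, using the remote-laboratory provisions already in section 1.3. Record the stop date, the reason and any change in other glucose-lowering therapy.
- **Section 9.3.2:** add an analysis of all treated patients that uses these values, reported beside the per-protocol on-drug result.
- **Section 7.2:** leave the investigator's grounds for stopping the drug or ending participation as they are.

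The cost is a short amendment, one local blood draw and one contact for each patient who stops, and possibly a smaller effect in the all-treated analysis. The change helps only patients who have not yet reached month 12. Section 5.6 reports 11 enrolled, which leaves up to 20 − 11 = 9 further places. At least the five patients in the published report have already contributed 12-month data, and the documents do not say how many of the others have passed that point.

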7.3 LOST TO FOLLOW-UP

A participant will be considered lost to follow-up if he or she fails to return for 1 scheduled visit and is unable to be contacted by the study site staff.

The following actions must be taken if a participant fails to return to the clinic for a required study visit:

- The site will attempt to contact the participant and reschedule the missed visit within 6 months and counsel the participant on the importance of maintaining the assigned visit schedule and ascertain if the participant wishes to and/or should continue in the study.

Abbreviated Title: Effects of leptin in insulin resistance

Version Date: AM N ver. (approved 10/21/20); rev for AM O (5/5/21)

- Before a participant is deemed lost to follow-up, the investigator or designee will make every effort to regain contact with the participant (where possible, 2 telephone calls and, if necessary, a certified letter to the participant's last known mailing address or local equivalent methods). These contact attempts should be documented in the participant's medical record or study file.
- Should the participant continue to be unreachable, he or she will be considered to have withdrawn from the study with a primary reason of lost to follow-up.

